11.1.4 Life-threatening (21 CFR 312.32(a))

An adverse event or suspected adverse reaction is considered “life-threatening” if, in the view of either the Sponsor-Investigator or Principal Investigator, its occurrence places the subject at immediate risk of death. It does not include an adverse event or suspected adverse reaction that, had it occurred in a more severe form, might have caused death.

11.2 Relationship to Study Drug

Association or relatedness to the study agent, study procedures and the subject's pre-existing disease will be graded as follows:

1. Definitely related
2. Probably related
3. Possibly related
4. Unlikely related
5. Unrelated

If the relationship between the AE/SAE and the investigational product is determined to be “possible” or “probable”, the event will be considered to be related to the investigational product for the purposes of expedited regulatory reporting.

11.3 Time Period and Frequency for Event Assessment and Follow-Up

11.3.1 Obligations of the Principal Investigator

All serious adverse events should be reported to the Sponsor-Investigator regardless of severity, relatedness, or expectedness. The Principal Investigator will provide an electronic report to the Sponsor-Investigator who will report to the Reviewing IRB on any serious adverse event that is both unexpected and related to the use of the corticosteroid product (i.e. there is reasonable possibility that the event may have been caused by the use of the product; the Principal Investigator will not await definitive proof of association before reporting such events).

The Principal Investigator will adhere to any other serious adverse event reporting requirements in accordance with federal regulations, state laws, and the local institutional policies and procedures, as applicable.

The Principal Investigator will be responsible for ensuring that the reporting requirements are fulfilled and will be held accountable for any reporting lapses.

11.3.2 Safety Reporting

All serious adverse events that are **unexpected** and **possibly, probably, or definitely related** to the use of either study drug should be reported to the Sponsor-Investigator within **48 hours** of the Principal Investigator's initial receipt of the information. All other serious adverse events

should be reported to the Sponsor-Investigator within **7 days** of the Principal Investigator's initial receipt of the information.

The Sponsor-Investigator will report serious adverse events that are unexpected and possibly, probably, or definitely related to the use of either study drug to the Reviewing IRB according to regulatory requirements described as follows:

Any serious adverse event that is fatal or life-threatening, that is unexpected and related to the use of either study drug will be reported to the Reviewing IRB as soon as possible, but not later than **3 business days** after the Sponsor-Investigator's initial receipt of the information.

Serious adverse events that are unexpected and related to the use of either study drug, but are not fatal or life-threatening, will be reported to the Reviewing IRB as soon as possible, but not later than **3 business days** after the Sponsor-Investigator's initial receipt of the information.

If, after further evaluation, an unexpected serious adverse event initially considered not to be related to the use of either study drug is subsequently determined to be related, then the event will be reported to the Sponsor-Investigator within **48 hours** of the determination. The Sponsor-Investigator will report to the Reviewing IRB within **3 business days** of the Sponsor-Investigator learning of the determination.

Relevant additional clinical and laboratory data will become available following the initial serious adverse event report. Principal Investigators must report follow-up information to the Sponsor-Investigator within **48 hours** of initial receipt of the information. All follow-up information relevant to a serious adverse event that is unexpected and related to the use of either study drug will be reported to the Reviewing IRB within **3 business days** of the Sponsor-Investigator's initial receipt of the information.

If a serious adverse event occurs within 30 days after a subject's final study visit and is determined to be unexpected and related to the use of either study drug, that event will be reported to the Reviewing IRB within **3 business days** of the Sponsor-Investigator learning of the determination.

Should a serious adverse event deemed possibly, probably or definitely related to the study agent occur during administration, the study agent will be discontinued, appropriate treatment will be given under medical supervision and the subject will be examined as frequently as necessary thereafter until symptoms cease or stabilize.

All new information and significant noncompliance indicating a new or increased risk or new safety issue as defined in the Reviewing IRB policies will be reported to the Sponsor-

Investigator within **48 hours** of the Principal Investigator learning of the information. The Sponsor-Investigator will report to the Reviewing IRB within **3 business days** of the Sponsor-Investigator's initial receipt of the information. This includes deviations from the protocol that harmed subjects or others or that indicates subjects or others might be at an increased risk of harm.

The Sponsor-Investigator will inform the Clinical Safety Monitor of all serious adverse events regardless of severity, relatedness, or expectedness and of all instances of significant non-compliance impacting patient safety within **48 hours** of the Sponsor-Investigator's initial receipt of the information.

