8.5 Subject Withdrawal Criteria

Subjects meeting the following criteria will be withdrawn from the trial:

1. Unable to tolerate study medication.
2. Failure to keep an accurate medication log.
3. Failure to keep study appointments.
4. Missing more than 10% of prescribed doses of study medication.*

**If a subject is missing more than 10% of prescribed doses, a discussion about the subject's continuation in the trial will take place between the Principal Investigator and the Sponsor-Investigator.*

Corticosteroids are the standard of care for the treatment of Duchenne muscular dystrophy and have a well-known side effect profile (see section 9.3). Subjects with any Grade 1 or higher (according to the Common Terminology Criteria for Adverse Events (CTCAE) version 4.03 and listed in section 11.1) adverse events that are anticipated and related to prednisolone use, will continue in the trial. Subjects with any Grade 2 or higher adverse events that are anticipated and are possibly, probably or definitely related to spironolactone use will have the study drug held and will be re-challenged in 1 week. If a subject experiences a recurrence of the adverse event, he may be withdrawn after discussion with the Clinical Safety Monitor. Subjects with any Grade 2 or higher adverse events that are unanticipated, may be withdrawn after discussion with the Clinical Safety Monitor. The Principal Investigator will determine a clinically appropriate tapering regimen with respect to assigned study drug and length of time on drug.

Principal Investigators must report all participant withdrawals to the Sponsor-Investigator within 48 hours of learning of the withdrawal. The Sponsor-Investigator will then notify the Clinical Safety Monitor of the withdrawal within 3 business days of the Sponsor-Investigator learning of the withdrawal.

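### A serious adverse event not judged both unexpected and related may take up to 7 days to reach the Sponsor-Investigator and 9 to reach the Clinical Safety Monitor, against 2 and 4 days in the fast stream

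*Combined protocol and SAP*

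**What the plan says.** Section 11.3.2 (Safety Reporting) sets two limits for the site's first report of an SAE to the Sponsor-Investigator.

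- Fast stream, 48 hours: "All serious adverse events that are unexpected and possibly, probably, or definitely related to the use of either study drug should be reported" inside that time.
- Slow stream: any other SAE "should be reported to the Sponsor-Investigator within 7 days of the Principal" Investigator learning of it.

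The same section sets the next step: "The Sponsor-Investigator will inform the Clinical Safety Monitor of all serious adverse events regardless of severity, relatedness, or expectedness". The limit closes that sentence, which also covers significant non-compliance: "impacting patient safety within 48 hours of the Sponsor-Investigator's initial receipt of the information".

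Other site-to-sponsor limits are all 48 hours:

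- SAE follow-up (11.3.2): "Principal Investigators must report follow-up information to the Sponsor-Investigator within 48 hours of initial receipt of the information". It is not tiered by cause or expectedness.
- Information pointing to a new or increased risk (11.3.2).
- Every participant withdrawal, whatever the reason (8.5).

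Section 11.1.3 treats any Grade 3, 4 or 5 event as serious. Section 11.4 lists raised potassium among the anticipated effects of spironolactone. The design is open label, at four to seven centers with about three boys each (7.2).

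**The concern.** The stream is chosen by a site investigator who knows the treatment and decides both cause and expectedness. If either answer is no, the event moves to the 7-day limit. A death called unrelated falls there. So does a related Grade 3 event that the site regards as an anticipated drug effect.

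Central receipt matters more than usual here. With about three boys per site, no single site is likely to see a pattern. Expedited reporting to the Reviewing IRB covers only SAEs that are unexpected and related (11.3.2), so for the slow stream the Clinical Safety Monitor is the main expedited independent check. The alternative is the monthly report and laboratory review (12.1, 12.1.1). Section 11.3.2 itself provides for an event first considered unrelated being reclassified later, so the protocol accepts that the first judgement can be wrong. Under the slow limit, the people placed to question that judgement may not see the event for a week or more.

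**Working it through.** The protocol prints each limit but not the total delay, so there is no stated total to reproduce. The check adds consecutive limits.

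| Step | Limit | Clock starts at | Section |
|---|---|---|---|
| Site to sponsor, unexpected and related SAE | 48 h = 2 days | site's receipt | 11.3.2 |
| Site to sponsor, any other SAE | 7 days | site's receipt | 11.3.2 |
| Sponsor to Clinical Safety Monitor, every SAE | 48 h = 2 days | sponsor's receipt | 11.3.2 |
| Site to sponsor, SAE follow-up | 48 h | receipt of the follow-up data | 11.3.2 |
| Site to sponsor, new-risk information | 48 h | site learning of it | 11.3.2 |
| Site to sponsor, withdrawal | 48 h | site learning of it | 8.5 |

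Maximum time to the monitor = site-to-sponsor limit + sponsor-to-monitor limit.

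- Slow stream: 7 + 2 = 9 days.
- Fast stream: 2 + 2 = 4 days.
- Difference: 9 − 4 = 5 days, all of it in the first step (7 − 2 = 5). The slow first step is 7 / 2 = 3.5 times the fast one.

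**Which events are slow.** Crossing expected/unexpected with related/unrelated gives four categories. Only unexpected and related is fast, so three of the four are slow. That counts categories, not events. The documents give no SAE counts or expected shares, so the proportion of events affected cannot be computed.

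**Comparison with the other 48-hour limits.** A withdrawal for missed appointments is due at the Sponsor-Investigator by day 2 (8.5). A death called unrelated is due by day 7, unless the site also reports it as a withdrawal; death is not among the withdrawal criteria listed in 8.5.

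**Routes out of the slow stream.**

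- Under 11.1.2 a known toxicity of greater severity or specificity counts as unexpected. If related, it becomes fast.
- Under 11.3.2 an unexpected SAE later judged related is due within 48 hours of that determination.
- New-risk information is due within 48 hours (11.3.2).
- An event that leads to withdrawal is signalled within 48 hours, and the monitor hears of the withdrawal within 3 business days after the sponsor does (8.5).

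These routes shorten the delay for some events, but most of them turn on a further judgement that the site will usually make first.

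**The case against.** The strongest reply is that tiered reporting is a legitimate design choice. The limits are maxima, the steps run in sequence and can all be met, and the routes above catch many events of concern. Sections 11.3.1 and 18.2 add federal, state and local reporting duties. All of this stands, and it makes the point an improvement rather than an error.

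A reader might also infer more than the documents support.

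- **That most SAEs are slow.** No count or share is given.
- **That follow-up can fall due before the first report.** Section 11.3.2 introduces follow-up as data arriving after the initial report, with its own clock from receipt of those data. The limits are uneven but do not contradict each other.
- **That the monitor's 48 hours is defeated.** That clock starts at the Sponsor-Investigator's receipt and can be met in full.
- **That a boy could be re-exposed before the monitor knows.** Section 8.5 concerns "Subjects with any Grade 2 or higher adverse events that are anticipated and are possibly, probably or definitely related to spironolactone use". These boys, it says, "will have the study drug held and will be re-challenged in 1 week". Seven days to the sponsor equals that week. Only the 9 days to the monitor exceeds it, by 2 days, and only if the hold and the site's receipt fall on the same day. The overlap with SAEs is confined to anticipated, spironolactone-related events of Grade 3 or higher. For these, 11.3.2 says that the agent is discontinued when a related SAE occurs during administration, so the re-challenge rule may not apply. Where 8.5 does apply, it calls for the monitor on recurrence, not before re-challenge, so earlier notice would change no required step.
- **That further boys could be randomised in the meantime.** The enrollment halt in 11.4 needs an event of Grade 3 or higher that is unanticipated and related, which in principle belongs to the fast stream. Faster reporting of the other SAEs would not trigger that halt sooner.
- **That the monitor is the only outside reviewer.** The Reviewing IRB also has a role (11.4), although expedited reports to it are limited to unexpected and related SAEs.

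**Conclusion.** The point holds as a cheap improvement. An SAE that the site does not judge both unexpected and related may take up to 7 days to reach the Sponsor-Investigator and up to 9 to reach the Clinical Safety Monitor, which is 5 days more than in the fast stream at each step. This is out of line with the 48-hour limits used for follow-up, new-risk information and withdrawals, and it makes the speed of independent review depend on one unblinded local judgement.

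The 9 days assumes that both parties use their full limit and that none of the routes to faster reporting applies. It is a worst case, not an expected delay. No stated rule is broken. The benefit claimed is only that the sponsor and the monitor could check the site's call on cause and expectedness up to 5 days sooner.

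**What to change.** In 11.3.2, apply the existing 48-hour limit to every SAE report from site to Sponsor-Investigator. Keep expectedness and relatedness only for deciding what goes to the Reviewing IRB. The maximum time to the monitor then becomes 2 + 2 = 4 days for all SAEs, and the IRB limits need no change.

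The cost is one sentence in an amendment and a few earlier site reports among 24 boys. Some first reports will be less complete, but the follow-up rule already provides for later data.

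Separately, the hold and re-challenge text in 8.5 and the discontinuation text in 11.3.2 give different instructions for an anticipated, spironolactone-related event of Grade 3 or higher that occurs during administration. The sponsor must reconcile the two sections. This change neither depends on how that is settled nor settles it.

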11.3.3 Serious Adverse Event Reporting: Content and Format

The serious adverse event report will include, but need not be limited to: (1) the date of the event; (2) designation of the report as an initial report or a follow-up report, identification of all safety reports previously filed for the clinical protocol concerning a similar adverse event, and an analysis of the significance of the adverse event in light of previous similar reports; (3) clinical site; (4) the Principal Investigator; (5) study drug; (6) route of administration e.g. intravenous or oral; (7) dosing schedule; (8) a complete description of the event; (9) relevant clinical observations; (10) relevant clinical history; (11) relevant tests that were or are planned to be conducted; (12) date of any treatment of the event; and (13) the suspected cause of the event. These items will be reported electronically to the Sponsor-Investigator who will then report to the Reviewing IRB as appropriate.

11.3.4 Communication Plan with the Primary Care Physician

Close communication should be established with the primary care physician of all study subjects and will be maintained throughout the trial if necessary. The important hallmarks of the trial will be explained. We may request laboratory reports, hospitalizations, clinical notes and any other relevant medical records pertaining to intercurrent events taking place during this 6-month study. The Principal Investigator will initiate an investigation to determine the possibility of an adverse event related to this trial and will adhere to the adverse event reporting requirements in accordance with federal regulations, state laws, and the local institutional policies and procedures, as applicable.

During the consent process, the Principal Investigator or designated Co-Investigator will emphasize the importance of subject communication with our study team. Any routine or non-routine doctor's visits or medical care received during the 6 months of this trial should be reported to the study team. The Study Doctor will explain to the subject that copies of any relevant medical records of those visits will be requested from their medical care provider.

11.3.5 Follow-Up of Adverse Events

All adverse events will be followed until resolution or stabilization.

11.4 Study Discontinuation Rules

An independent Clinical Safety Monitor will monitor safety data on a continual basis throughout the trial. The Clinical Safety Monitor can recommend early termination of the trial for reasons of safety. Study enrollment will be halted by the Principal Investigators when any subject experiences a Grade 3 or higher adverse event toxicity that is unanticipated and possibly, probably, or definitely related to the study drug that presents with clinical symptoms and requires medical treatment. This will include any subject death, hospitalization, or important clinical laboratory finding. If after review by the Clinical Safety Monitor and the Reviewing IRB, the decision is made to continue, the trial will proceed according to Section 10 of this protocol.

Anticipated adverse events related to progression of Duchenne muscular dystrophy may include muscle weakness, elevated creatine kinase levels, loss of ambulation, scoliosis, short stature, and intellectual disability.

Anticipated adverse events related to prednisolone treatment, which is the standard of care, may include weight gain, cushingoid features, long bone fractures, acne, behavioral disturbance, and short stature (see section 9.3.2 for additional potential side effects).

Anticipated adverse events related to spironolactone treatment may include increased potassium levels, increased breast tissue mass, diarrhea, cramping, nausea, vomiting, headache, sleepiness, unsteadiness, and urticaria (see section 9.3.1 for additional potential side effects).

12. CLINICAL MONITORING

12.1 Data Safety Monitoring Plan

[name] will serve as Clinical Safety Monitor for this trial. [name] is a pediatric pulmonologist and critical care specialist at NCH, and an Associate Professor of Pediatrics at the Ohio State University. [name] will be asked to review all subjects' laboratory results monthly. He will be apprised of all adverse events, as per the Reviewing IRB policy. He will prepare interim safety reports 3 months and 6 months after the first subject is dosed and a final safety report after all subjects complete 6 months of dosing. The Clinical Safety Monitor can recommend early termination of the trial for reasons of safety.

The Clinical Safety Monitor's responsibilities are to:

- review the plans for data and safety monitoring;

- consider factors external to the study when relevant information becomes available, such as scientific or therapeutic developments that may have an impact on participant safety or the ethics of the trial;
- review study performance, make recommendations and assist in the resolution of problems reported by the Principal Investigators;
- review monthly safety data to determine safety signals or trends;
- ensure the confidentiality of the trial data; and,
- assist by commenting on any problems with study conduct, enrollment, and sample size and/or data collection.

12.1.1 Safety Monitor Reporting

Reports describing the status of the study will be prepared by the Sponsor-Investigator and associated staff and sent to the Clinical Safety Monitor the end of each month, or at the Clinical Safety Monitor's request.

Reports will include the following:

- A brief narrative of the trial status, including the target enrollment, current and projected time to completing enrollment. Any significant events and/or difficulties should be briefly described in this narrative;
- A brief narrative for each subject describing age, race and ethnicity and other relevant demographic characteristics. The narrative for each subject should briefly describe his study status (i.e., dose level, visit number, adverse event information);
- A timeline outlining the trial progress relative to visit number for each subject, as well as time points for each SAE. A total for Adverse Events (AEs) for each subject should be included;
- A summary of AEs by classification;
- A listing of AE details grouped by subject;
- A listing of SAE details grouped by subject;
- A listing of deaths;
- A summary of clinically significant laboratory test results;

12.2 Institutional Review Board Monitoring & IRB Reliance

The Principal Investigators will obtain IRB approval for the investigation. Initial IRB approval, and all materials approved by the Reviewing IRB for this trial, including the subject's consent forms and recruitment materials, must be maintained by the Principal Investigators and made available for inspection.

The NCH IRB has offered to serve as the Reviewing IRB for all institutions via SMART IRB. Participating sites of this protocol are encouraged to utilize this infrastructure to expedite the review process. Participating sites will need to be existing members of the SMART IRB Master

Common Reciprocal Institutional Review Board Authorization Agreement to utilize the NCH IRB as their IRB of record. Sites that use the single IRB will rely on the NCH IRB approval in order for all study sites to have the same IRB determination, consent template(s), and expiration date.

Sites that choose not to use the NCH IRB as IRB of record must provide the Coordinating Center with a copy of the initial IRB protocol approval and the yearly IRB continuing reviews.

Modifications will be submitted to the NCH IRB for their review and approval prior to implementation. When a modification to a protocol substantially alters the study design or increases potential risk to the study subject, the informed consent form will be revised and if applicable, subject's consent to continue participation will again be obtained.

